Cover Page for Clinical Trial Study

Official Title: The Effect of Animal-Assisted Therapy on Prosocial Behavior in Children with Developmental Delay or Autism Spectrum Disorder

NCT #: N/A

Date: November 11, 2024

Study Protocol

Clinical Study Description

The purpose of this study is to investigate the effect of animal-assisted therapy (AAT) on prosocial behavior and emotional regulation, both during and after AAT sessions, in children referred for an autism spectrum disorder (ASD) evaluation or documented developmental delay (DD) or behavioral concerns. We seek to address identified gaps in knowledge of the use of canines in therapy sessions by analyzing short- and long-term effects of AAT and human-animal interaction occurring in AAT sessions. Caregivers were given the option to enroll the child in the AAT study at the follow-up appointment after the diagnostic assessment was completed, or upon enrollment in the ASD program if the child had an ASD diagnosis. Each AAT study lasted between eight to 12 weeks, and caregivers had the option to re-enroll the child for the next study to continue addressing behavioral concerns. Animal-assisted therapy sessions lasted 30 to 45 minutes, depending on the age and ability of the participant. Sessions started with five to 10 minutes of free play with the canine, followed by sensory integration therapy based on the child's identified sensory profile. Participants then entered the clinic room for 20 to 30 minutes of a seated activity in which the therapist, a certified pediatric nurse practitioner (CPNP), taught coping and socialization strategies to participants and caregivers. Sessions concluded with five minutes of play with the canine. Play activities include fetch, soccer, hide and seek, and puzzles. The canine was trained to lay under the table in the clinic room while the therapist was working with the participants. He would provide grounding, light pressure, and deep pressure therapy if the participant became anxious during the sessions. The seated work was recorded using two cameras to ensure visibility of the interactions between the participant and therapist, canine, and caregiver; participant vocalizations and verbalizations; and participant facial expressions. We used two human-animal ethograms to code behavior during sessions and two behavioral assessments to note behavior occurring after sessions. All sessions occurred in the clinic located on the university's campus. Demographic data including participant age, gender, race, ethnicity, referral source, prior medical diagnoses, age of ASD or DD diagnosis, medications, and prior allied health, school, or psychological evaluations. The canine was trained as a therapy dog and was being trained as a service dog at the time of the study. The canine was present during sessions to interact with children and assist them to practice and develop skills to address identified deficits in social-emotional and adaptive functioning, prosocial behavior, and emotional regulation. AAT sessions were recorded to code interactions at a later time.

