
Objectives

1. Do interactions between a trained therapy canine and autistic children differ depending on the child's verbal abilities?
2. Is there a difference in prosocial behavior and emotional regulation in AAT sessions among children with varying verbal abilities?
3. Is there a difference in prosocial behavior and emotional regulation apart from animal-assisted therapy sessions among children with varying verbal abilities?

Design

We used standardized instruments to investigate human-animal intervention (HAI) occurring during AAT sessions and prosocial behavior and emotional regulation demonstrated by participants outside of AAT sessions. SPSS and Microsoft Excel were used to run the analysis. Descriptive statistics were utilized to compare prosocial behavior and emotional regulation occurring apart from AAT sessions between the two groups based on the self-report questionnaires completed by caregivers. Independent t-tests were used to analyze the differences in human-animal interaction among children with ASD with varying verbal abilities from the recorded sessions. The homogeneity of the variance (HOV) assumption between two groups was checked using Levene's test for equality of variances in SPSS program before conducting the t-tests analysis. Results of t-tests with adjusted degrees of freedom value were reported if the HOV was violated. The null hypothesis was set to reflect no significant difference in HAI between verbal and nonverbal groups for the independent t-tests; therefore, a significant difference in the human-animal interaction behaviors regarding the children's verbal abilities could be confirmed if the t-test results reject the null hypothesis. Cohen's d was used to report the effect sizes of the independent t-tests; values up to 0.20 were interpreted as small, 0.50 as medium, and 0.80 as large effect sizes.

Methods

Demographic data; past, family, and social histories; and prior therapy evaluations were collected during the initial consultation for enrollment into the ASD program.

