Lastly, the Positive and Negative Affect Schedule (PANAS) was administered weekly to measure therapeutic effects occurring in everyday life outside of the AAT session. The PANAS is a 20-item questionnaire utilizing a 5-point Likert scale to assess positive and negative affect occurring the week prior to administration. Each domain has 10 items with scores ranging from 10 to 50, with lower scores reflecting lower levels of positive or negative affect and higher scores signifying higher positive or negative affect²⁹. Total scores on each scale are obtained by adding the scores for each item. Analysis of the PANAS demonstrates very good internal consistency reliability, with alphas ranging from 0.86 to 0.90 for Positive affect and from 0.84 to 0.87 for Negative affect.

Statistical Analysis Plan

This present study used standardized instruments to investigate human-animal interaction (HAI) occurring during AAT sessions and prosocial behavior and emotional regulation demonstrated by participants outside of AAT sessions. SPSS and Microsoft Excel were used to run the analysis. Descriptive statistics were utilized to compare prosocial behavior and emotional regulation occurring apart from AAT sessions between the two groups based on the self-report questionnaires completed by caregivers. A total of 144 sessions were conducted, 84 of which were recorded and coded to analyze HAI during sessions. Independent t-tests were used to analyze the differences in human-animal interaction among children with ASD with varying verbal abilities from the recorded sessions. The homogeneity of the variance (HOV) assumption between two groups was checked using Levene's test for equality of variances in SPSS program before conducting the t-tests analysis. Results of t-tests with adjusted degrees of freedom value were reported if the HOV was violated. The null hypothesis was set to reflect no significant difference in HAI between verbal and nonverbal groups for the independent t-tests; therefore, a significant difference in the human-animal interaction behaviors regarding the children's verbal abilities could be confirmed if the t-test results reject the null hypothesis. Cohen's d was used to report the effect sizes of the independent t-tests; values up to 0.20 were interpreted as small, 0.50 as medium, and 0.80 as large effect size.

Protocol Number: 2201382953
Investigator: [name]

Expiration Date: 03/31/2024
Last Approval Date: 04/01/2023

University of Arkansas System

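### Letting Levene's test choose between the pooled and adjusted t-test does not hold a 5% error rate when the verbal groups differ in size; the direction depends on which group is more variable (minor)

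*Combined protocol and SAP*

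**What the plan says.** The Design section of the Study Protocol and the Statistical Analysis Plan section state the same rule.

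- The comparison: "Independent t-tests were used to analyze the differences in human-animal interaction among children with ASD with varying verbal abilities from the recorded sessions".
- The pre-test: "The homogeneity of the variance (HOV) assumption between two groups was checked" by Levene's test in SPSS before the t-tests.
- The switch: "Results of t-tests with adjusted degrees of freedom value were reported if the HOV was violated".

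The null hypothesis is "no significant difference in HAI between verbal and nonverbal groups". On the data, the SAP says: "A total of 144 sessions were conducted, 84 of which were recorded and coded to analyze HAI during sessions". The Clinical Study Description adds that sessions repeat within a child: "Each AAT study lasted between eight to 12 weeks, and caregivers had the option to re-enroll the child for the next study".

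The documents do not give the number of children or sessions in each verbal group, the SDs, the significance level, the Levene threshold, or whether the session or the child is the unit of analysis. The Subjects table of the IRB protocol summary lists 20 children, which is an application count and not an analysed sample.

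**The concern.** Levene's test has limited power in small or unbalanced samples. When it fails to reject, the pooled t-test is kept, including in data sets where the variances do differ. The pooled standard error is then wrong if the groups also differ in size. Verbal ability is an observed trait and is not allocated, so there is no reason to expect equal groups.

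The rule governs every t-test in the plan, and these are its only inferential analyses. If the smaller group is the more variable, more than 5% of true null comparisons would be declared significant. If the larger group is, the tests lose power without anyone noticing.

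**Working it through.** There is no stated figure to reproduce: the documents contain no alpha, power, sample-size calculation, group sizes or SDs.

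**Assumptions.** Two-sided 5% test; mean-centred Levene test at 5%; adjusted degrees of freedom taken as the Welch-Satterthwaite result. Totals are 84 units (the coded sessions) or 20 units (children in the application). Group splits and SD ratios are illustrative. The SD ratio is the smaller group's SD divided by the larger group's.

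**Step 1. Why direction matters.** The true variance of the mean difference is s1²/n1 + s2²/n2. The pooled test estimates it by [((n1−1)s1² + (n2−1)s2²)/(n1+n2−2)] × (1/n1 + 1/n2).

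- 5 vs 15, SDs 2 and 1: true 4/5 + 1/15 = 0.867; pooled (30/18) × 0.267 = 0.444. The true SE is √(0.867/0.444) = 1.40 times the pooled SE, so the test is too liberal.
- 5 vs 15, SDs 1 and 2: true 1/5 + 4/15 = 0.467; pooled (60/18) × 0.267 = 0.889. The factor is 0.72, so the test is too conservative.
- 10 vs 10, SDs 2 and 1: true 0.5; pooled 2.5 × 0.2 = 0.5. There is no distortion.
- 14 vs 70, SDs 2 and 1: true 0.300; pooled (121/82) × 0.0857 = 0.1265. The factor is 1.54. As 1.96/1.54 = 1.27, always pooling would reject about 20% of the time, which agrees with a simulated 20.3%.

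**Step 2. Error of the plan's rule.** Equal means, normal independent data, 100,000 simulated data sets per row:

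| Split (smaller:larger) | SD ratio | Two-stage rule | Welch always |
|---|---|---|---|
| 42:42 | 0.5 to 3 | 4.9-5.0% | 4.9-5.1% |
| 28:56 | 1.5 | 6.0% | 5.0% |
| 21:63 | 1.5 | 6.9% | 5.1% |
| 14:70 | 1.5 | 8.3% | 4.8% |
| 28:56 | 2 | 5.2% | 5.0% |
| 21:63 | 2 | 5.5% | 5.0% |
| 14:70 | 2 | 6.8% | 5.2% |
| 7:13 | 2 | 8.2% | 5.1% |
| 5:15 | 2 | 11.4% | 5.5% |
| 5:15 | 0.5 | 2.4% | 4.9% |

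With the larger group more variable (ratio 0.67), the rule gives 4.4% at 28:56, 3.9% at 21:63 and 3.5% at 14:70. With 20 units and a two-fold SD ratio, Levene rejects only about 40% of the time, so the pooled test is usually kept. At 14:70 it rejects about 86% of the time for the same ratio, which is why the excess shrinks there. A simulated bounded 0-36 bond score showed the same pattern as the normal data.

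**Step 3. Repeated sessions.** Take 14 children × 6 sessions = 84, with an assumed within-child correlation (ICC) of 0.1, 0.3 or 0.5. Treating sessions as independent, Welch gives about 11%, 22% and 31%, and the two-stage rule gives nearly the same. Welch on one mean per child gives 4.5% to 6.2%.

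**Step 4. Skewed counts.** Negative binomial, assumed mean 3, 14:70. At SD ratio 1.32 the two-stage rule gives 6.5% and Welch 10.4%. At ratio 2.35 they give 16.8% and 15.0%. Neither holds 5%, and Welch is not reliably the better of the two.

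**The case against.** Testing for equal variances and then switching is a common, openly stated rule, and it already removes most of the harm. At 14:70 with SD ratio 2, always pooling gives 20.3% and the plan's rule 6.8%. At 84 units the excess is about 0 to 3.5 percentage points, and it is largest at moderate SD ratios. The larger figures need about 20 units and a marked imbalance. All of this stands, and it limits the severity.

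A reader might infer that any difference in size and spread inflates false positives. It does not: inflation requires the smaller group to be the more variable, and the opposite pattern makes the rule conservative. A reader might also infer that this trial's results are inflated. The documents give neither group sizes nor SDs, so they do not show it. Because the bond score includes talking to the canine, spread may well differ between verbal groups, but that does not say which group is smaller.

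Finally, one might conclude that Welch should be used for every comparison. The methods section describes tally counts, durations rounded to 30 seconds and a modal intensity code from 0 to 3. For skewed counts Welch can do worse than the plan's rule, so that remedy goes too far.

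**Conclusion.** The concern holds in a limited form. With unequal verbal groups the Levene switch does not hold an assumed 5% level for roughly normal scores. The error rate is about 6% to 8% at 84 sessions with SD ratio 1.5, and up to about 11% at 5 versus 15 children with ratio 2, when the smaller group is the more variable. It falls below 5% when the larger group is, and is essentially unaffected when the groups are equal. Splits, SD ratios, alpha and the Levene threshold are all assumptions.

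Severity is minor. Analysing repeated sessions as independent would cost far more (about 11% to 31% at the ICCs assumed), and changing the t-test variant does nothing about that.

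**What to change.** In the Design and Statistical Analysis Plan sections:

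1. Drop the Levene switch. For roughly symmetric scores such as the 0-36 bond score, report the unequal-variance (Welch) result by default, applied to one summary value per child. Alternatively, fit a model with a child effect and allow the residual variance to differ by verbal group.
2. For tally counts, rounded durations and the 0-3 intensity mode, do not rely on Welch alone. Use a count or ordinal model that accounts for the child, or a permutation test that reassigns whole children.
3. State alpha and the unit of analysis, and report children, sessions and SDs by verbal group, so that a reader can see which case applies.

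Cost: SPSS already prints the unequal-variance row, and no new data are needed. If variances are truly equal, some power is lost: 66% against 71% for 14 vs 6 at d = 1.3, and 68% against 69% for 60 vs 24 at d = 0.6. The plan is written in the past tense, so a change of wording is not enough. Results already reported would need re-reporting, with the change identified as made after the fact.

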The Observation for Human Canine Interaction for Research (OHAIRE) Coding System from University of Arizona was used to note human bonding and prosocial behavior occurring during AAT sessions. The OHAIRE Coding System was specifically created for use in research with participants aged 4 to 16 years but may also be suitable for individuals of other ages, provided appropriate validity and reliability analyses are conducted. Participants must be with at least one other person during sessions to allow for the coding of social behaviors. The participant being observed is known as the primary participant. The coding system allows for the primary participant to engage in social behaviors with various targets, including caregivers, therapists, objects, and canines. While the OHAIRE was designed to code behavior in the presence of common domesticated canine species, it has been tested with a restricted range of canine species to date. The tool has previously been used to code interactions with dogs and guinea pigs, as well as social behaviors before and after interactions with horses (not direct interactions with horses). The coded behaviors are general enough to be assumed to apply to other domesticated canine species. Participants were video recorded continuously during unstructured interaction opportunities. Available activities provided opportunities to engage in both social and isolated behaviors. The video sample included a wide enough angle to observe the environment and all potential social interaction partners. The OHAIRE-V3 calculates a human-canine bond score in order to quantify the interactions taking place between the primary participant and the canine. The human-canine bond score was calculated for each 10-second interval based on the presence of an interaction between the primary participant and the canine, and the type of behaviors shown during that interaction. Participants received one point for each of the six behaviors from the 'social communication & interaction' category in the OHAIRE tool. No points were given if the primary participant does not interact with the canine. The behaviors included in the definition of the human canine bond score are talk, gesture, look, touch, affection, and prosocial behavior directed toward the canine. There are a total of six 10-second intervals within each 1-minute video segment, and each of those 10-second intervals has six possible points: one point for each type of interaction. The total score from each 10-second interval is summed for a total overall human-canine bond score across the entire 1-minute video segment. Each 10-second interval will have a score between 0 and 6 points. Each 1-minute video segment will have a score between 0 and 36 points.

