
The 3-AAT Observation ethogram, adapted with permission from Johns Hopkins University, was used to code both canine and human interaction during AAT sessions. The revised ethogram appraises the frequency of six domains of human interaction (affection, play, care, communication, comfort, withdrawal) and 24 subdomains of human behavior that can occur in an AAT session as seen in Table 1. The ethogram assesses the frequency, intensity, and duration of the interactions between the canine and child. Frequency is measured by a tally count and duration is assessed by rounding either up or down to the nearest 30 second mark. Each interaction has a code for intensity from 0 (not intense) to 3 (the most intense), and the mode of the interaction was entered to run the analysis.

The Strengths and Difficulties Questionnaire (SDQ) is a 25-item tool developed to assess five domains: Emotional Problems, Conduct Problems, Hyperactivity, Peer Problems, and Prosocial. The SDQ is the most used instrument in measuring therapeutic effect of interventions within the emotional state in children and adolescents ages 2 to 18 years, demonstrating reliable internal consistency and validity. The SDQ has two versions, one to be administered at the initiation of therapy and then a follow-up version that includes two additional questions examining the impact of the therapeutic intervention. Scores from four behavioral domains range from zero ("normal") to 10 ("very high concerns"), while Prosocial domain scores are reversed so that 10 indicates "normal" behavior and zero signifies "very high concerns". The SDQ also assesses the total, impact, internalizing, and externalizing scores to provide a complete overview of the child's behavior during the past four weeks. Total scores are the sum of the behavior domains except the Prosocial domains and range from zero (normal) to 40 (very high). Impact scores range from zero (normal) to 10 (very high) and reflect overall distress and impairment interfering with daily social interactions. Internalizing scores reflect the Emotional Problems and Peer Problems domains, while Externalizing scores are the sum of the Conduct Problems and Hyperactivity domains. Both the Internalizing and Externalizing domain scores range from zero (normal) to 20 (very high). The initial SDQ was administered at the beginning of the study and the follow-up assessment was used subsequently every four weeks until the study concluded.

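### The plan treats rejection by unlisted t-tests as confirming a verbal/nonverbal difference, without saying which or how many must reject, with no multiplicity control and no stated unit of analysis

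*Combined protocol and SAP*

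**What the plan says.** The Design section and the Statistical Analysis Plan describe the in-session comparison in almost the same words. One general null covers all the tests: "The null hypothesis was set to reflect no significant difference in HAI between verbal and nonverbal groups for the independent t-tests". The consequence of rejecting it is that "a significant difference in the human-animal interaction behaviors regarding the children's verbal abilities could be confirmed if the t-test results reject the null hypothesis". The question being answered is the first of three unranked objectives: "Do interactions between a trained therapy canine and autistic children differ depending on the child's verbal abilities".

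The Methods section offers several outcomes for these tests. The 3-AAT ethogram "appraises the frequency of six domains of human interaction (affection, play, care, communication, comfort, withdrawal) and 24 subdomains of human behavior", and "The ethogram assesses the frequency, intensity, and duration of the interactions between the canine and child". In addition, "The OHAIRE-V3 calculates a human-canine bond score in order to quantify the interactions taking place between the primary participant and the canine".

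On the data, the Statistical Analysis Plan says: "A total of 144 sessions were conducted, 84 of which were recorded and coded to analyze HAI during sessions". The t-tests draw on these recorded sessions. Levene's test and Cohen's d are specified. The text available for review gives no significance level, sidedness, list of tested variables, primary outcome, multiplicity rule, unit of analysis, or exploratory label for these tests. The out-of-session questionnaires (SDQ and PANAS) are compared descriptively, so they are not part of the t-test family.

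**The concern.** To call a difference confirmed, a reader must know what was tested and what result counts as success. Here one null about HAI in general stands for an unlisted set of tests, and nothing says whether one, some or all must reject. If more than one outcome was tested and any rejection was taken as enough, the chance of a false confirmed difference exceeds the level of each test.

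A second gap determines whether a simple remedy would work. Sessions were weekly (IRB questionnaire, duration and frequency), each study ran eight to 12 weeks, and children could re-enrol (Clinical Study Description), so a child can contribute several sessions. If the t-tests took sessions as independent observations, each p-value would tend to be too small before multiplicity arises. Adjusting such p-values would look like a repair without being one. The answer to Objective 1 is at stake.

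**Working it through.** The plan states no error rate, number of tests or power, so there is no figure of its own to reproduce. What follows are scenarios.

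**Inputs from the document.** Six ethogram domains, 24 subdomains, three metrics and one OHAIRE bond score (Methods); 84 coded sessions (Statistical Analysis Plan); 20 children (Subjects table of the IRB protocol summary, a planned count and not a stated analysis number).

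**Assumptions.** Two-sided alpha of 0.05, with 0.01 and 0.10 as the range; correlation between outcomes of 0, 0.5 or 0.8; within-child correlation of 0.05, 0.2 or 0.5; 10 verbal versus 10 nonverbal children with 4 or 5 sessions each.

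**Step 1: multiplicity alone.** Suppose that there is no true difference and each test holds its level. For k independent tests, the chance of at least one rejection is 1 − (1 − alpha)^k. With k = 6 and alpha = 0.05 this is 1 − 0.95^6 = 0.265. With k = 1 it is 0.05. For correlated outcomes, the same probability was obtained by numerical integration over equicorrelated normal test statistics. For six tests:

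| Alpha per test | Correlation 0 | 0.5 | 0.8 |
|---|---|---|---|
| 0.01 | 5.9% | 4.9% | 3.3% |
| 0.05 | 26.5% | 20.7% | 13.9% |
| 0.10 | 46.9% | 37.0% | 25.1% |

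Every entry exceeds its per-test alpha. Testing subdomains, intensity, duration or the bond score as well would raise it further.

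**Step 2: repeated sessions alone.** 84/20 = 4.2 sessions per child. Each child belongs to one group, so treating sessions as independent understates the variance of the group difference by about the design effect, 1 + (4.2 − 1) × r, where r is the within-child correlation. The actual error of a nominal 5% test is then about 2 × [1 − Φ(1.96/√design effect)].

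| r | Design effect | 1.96/√design effect | Approximate error | Simulated error |
|---|---|---|---|---|
| 0.05 | 1.16 | 1.82 | 6.9% | about 7% |
| 0.2 | 1.64 | 1.53 | 12.6% | about 13% |
| 0.5 | 2.60 | 1.22 | 22.4% | about 23% |

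At r = 0 the inflation vanishes.

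**Step 3: would Holm alone repair it?** In simulation, Holm was applied to six session-level t-tests. With uncorrelated outcomes, the family-wise error was between 8% and 9% at r = 0.05. At outcome correlation 0, 0.5 or 0.8 it was 22%, 18% or 12% at r = 0.2, and 50%, 40% or 27% at r = 0.5. Holm applied to one mean per child gave 5% or less throughout at r = 0.2 and 0.5. The analysis must respect the child as the unit before an adjustment means anything.

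**The case against.** The strongest reply is that the sentence is loose textbook wording for a null-hypothesis test. It says only that the t-test results reject; it does not say any of them. The number of tests is unknown, and a single test of the bond score would raise no multiplicity issue. This stands. A reader might infer that one rejection among many was enough, or that the false-positive risk is 26%. The document supports neither. The missing rule is the defect, and the figures are conditional.

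A reader might also infer that sessions were in fact analysed as independent. That is not shown either. Recorded sessions are named as the data source, and averaging per child is not excluded. The figure of 20 is an IRB count. The t-tests concern children with ASD, while enrolment also covers developmental delay and behavioural concerns, so the number analysed may differ. The within-child correlation is assumed.

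It can also be said that the study is exploratory, since the purpose statement in the IRB questionnaire speaks of exploring gaps in knowledge. That is a general aim, set beside different research questions. It does not label these tests, and the language of confirmation points the other way. Finally, the tests compare verbal with nonverbal children and make no treatment-efficacy claim. That limits the consequences but does not supply the missing rule.

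**Conclusion.** The concern holds in conditional form. The document lets a group difference be called confirmed without saying which tests were run, how many had to reject, or at what level. If six outcomes were tested at 5%, the chance of a false rejection is 14% to 26% over the outcome correlations considered; over alpha from 0.01 to 0.10 the range is 3% to 47%. If one outcome was tested, there is no multiplicity excess. Separately, if sessions were taken as independent and came from about 20 children, a single nominal 5% test has an actual error of about 7% to 23% for within-child correlation from 0.05 to 0.5. These results rest on normal data, no true difference and the assumptions listed. They do not show that any reported result is wrong. They show that the word confirmed is not earned by the rule as written. The correction is cheap and affects how Objective 1 is read, so it should be made.

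**What to change.** In both the Design section and the Statistical Analysis Plan:

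- Delete the sentence about confirming a difference on rejection.
- List every t-test run, with its outcome and metric.
- Label all of these tests exploratory.
- Report Cohen's d with 95% confidence intervals from an analysis that allows for repeated sessions: either one mean per child per outcome, or a mixed model with child as a random effect.
- State how many children, by group, contributed the 84 sessions.
- If p-values are kept, state alpha and sidedness and compute them at child level. Mark any Holm-adjusted family as post hoc and not confirmatory: the analyses are described in the past tense, so a family chosen now cannot give confirmatory error control.
- Note that the talk item of the bond score and the ethogram's communication domain partly reflect the variable that defines the groups.

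The cost is wording in two sections and a modest re-analysis of data already coded. No new data or recoding is needed. The downside is wider intervals and fewer results that can be called significant. Assuming 10 versus 10 children, 80% power requires a difference of about 1.3 standard deviations of the child means for one test at 0.05, and about 1.7 at the first Holm step for six tests (0.05/6 = 0.0083).

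### The Cohen's d labelling rule reads as upper limits and no interval is planned, so effects can be labelled up to one step too large with no measure of precision

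*Combined protocol and SAP*

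**What the plan says.** The rule appears twice in the combined protocol and SAP. The Statistical Analysis Plan section states that "values up to 0.20 were interpreted as small, 0.50 as medium, and 0.80 as large effect size", and the Design section gives the same cut-offs: "values up to 0.20 were interpreted as small, 0.50 as medium, and 0.80 as large effect sizes".

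d accompanies the t-tests ("Cohen's d was used to report the effect sizes of the independent t-tests"), and these use session data: "Independent t-tests were used to analyze the differences in human-animal interaction among children with ASD with varying verbal abilities from the recorded sessions". On the amount of data, the Statistical Analysis Plan says "A total of 144 sessions were conducted, 84 of which were recorded and coded to analyze HAI during sessions". The study description at the front adds that "Each AAT study lasted between eight to 12 weeks, and caregivers had the option to re-enroll", so one child can supply many sessions.

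Neither section mentions a confidence interval or standard error for d or for the mean difference. The documents also do not give the verbal/nonverbal split, the number of children analysed, the significance level or any observed d.

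**The concern.** A labelling rule should give every value of d exactly one label and reserve no-label for effects too small to matter. This one does neither. 'Up to' is written once, before 0.20, and most naturally carries over to 0.50 and 0.80. The values then become ceilings: there is no class for a negligible effect and none for an effect above 0.80. If 'up to' governs only 0.20, nothing says where small ends and medium begins, or where medium ends and large begins, and two analysts could label the same d differently.

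The second problem is precision. With few children and repeated sessions, d is estimated loosely. A bare d with an adjective tells the reader nothing about that. Objective 1 is the verbal v nonverbal comparison, so the adjective is likely to be carried into any description of how large that difference is.

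**Working it through.** There is no figure in the plan to reproduce: it states no power, SD or interval, and the cut-offs are conventions.

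**Step 1: what each reading of the rule does.** The second column is the rule read as upper limits. The third treats 0.20, 0.50 and 0.80 as the values where labels start. The fourth gives each d the label of the nearest value, so its boundaries are (0.20 + 0.50)/2 = 0.35 and (0.50 + 0.80)/2 = 0.65.

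| Absolute d | Upper limits | Lower limits | Nearest value |
|---|---|---|---|
| 0.01 | small | none | small |
| 0.25 | medium | small | small |
| 0.40 | medium | small | medium |
| 0.55 | large | medium | medium |
| 0.70 | large | medium | large |
| 0.90 | no label | large | large |

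Up to 0.80, the upper-limit reading is one step above the lower-limit reading throughout. Against the nearest-value reading it is one step higher only from 0.20 to 0.35 and from 0.50 to 0.65. Up to 0.80 neither alternative gives a higher label than the upper-limit reading. Above 0.80 that reading gives no label at all.

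**Step 2: precision of d.** Inputs: 84 coded sessions (Statistical Analysis Plan) and 20 children (Subjects table of the ethics application, a planned count rather than a number analysed). Assumptions: the group splits and the 95% level.

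Formula: SE(d) = sqrt[(n1 + n2)/(n1 n2) + d²/(2(n1 + n2))], interval d ± 1.96 SE.

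- Sessions, 42 v 42, d = 0.50: SE = sqrt(84/1764 + 0.25/168) = sqrt(0.0476 + 0.0015) = 0.222; interval 0.07 to 0.93.
- Sessions, 63 v 21, d = 0.50: SE = sqrt(84/1323 + 0.25/168) = 0.255; interval 0.00 to 1.00.
- Children, 10 v 10, d = 0.50: SE = sqrt(20/100 + 0.25/40) = 0.454; interval -0.39 to 1.39.
- Children, 15 v 5, d = 0.50: SE = sqrt(20/75 + 0.25/40) = 0.522; interval -0.52 to 1.52.

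Exact noncentral-t intervals agree to within about 0.02. The label bands are 0.20 to 0.30 wide; the narrowest of these intervals is 0.86 wide.

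**Step 3: repeated sessions.** If all 20 children contributed, there are 84/20 = 4.2 coded sessions per child, and the design effect is 1 + (4.2 - 1) × ICC. The ICC is not given, so the full range is shown, for equal groups and d = 0.50.

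| ICC | Design effect | Effective sessions | Half-width of 95% interval |
|---|---|---|---|
| 0 | 1.00 | 84.0 | 0.43 |
| 0.3 | 1.96 | 42.9 | 0.61 |
| 0.5 | 2.60 | 32.3 | 0.70 |
| 1 | 4.20 | 20.0 | 0.89 |

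**Step 4: how stable the label is.** Chance that the absolute observed d falls in each band, from the noncentral t distribution:

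| Data, true d | 0 to 0.20 | 0.20 to 0.50 | 0.50 to 0.80 | above 0.80 |
|---|---|---|---|---|
| 42 v 42, d = 0 | 64% | 34% | 2% | 0% |
| 42 v 42, d = 0.50 | 8% | 41% | 41% | 10% |
| 10 v 10, d = 0.50 | 19% | 29% | 25% | 27% |

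With no true difference and 84 independent sessions, d exceeds 0.20 about 36% of the time. On the upper-limit reading it would then be called medium or larger.

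**The case against.** The strongest reply is that this is only wording. The conclusion rests on the t-test: "a significant difference in the human-animal interaction behaviors regarding the children's verbal abilities could be confirmed if the t-test results reject the null hypothesis". The value of d is itself reported, so a reader can ignore the adjective, and no p-value moves. At 42 v 42 and a two-sided 5% level (assumed; none is stated), rejection needs an absolute d of about 0.43, so most of the null results in the 36% above would not be called confirmed. That stands, and it keeps this a reporting point. It does not repair the rule or supply the missing interval.

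A reader might infer more than the documents support:

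- *That effects were in fact labelled a step too large.* No observed d is given, and the sentence is elliptical. On the nearest-value reading only part of the range shifts.
- *That 144 sessions over 8 to 12 weeks means 12 to 18 children.* That quotient (144/12 to 144/8) counts courses. Re-enrolment means courses are not children, and the t-tests use 84 sessions. The only child count in the documents is 20.
- *That d itself is distorted by unequal variances or small-sample bias.* The plan adapts the test ("Results of t-tests with adjusted degrees of freedom value were reported if the HOV was violated") and does not say which SD standardises d. That is a gap, but nothing shows that the variances or group sizes differ. The small-sample factor 1 - 3/(4 df - 1) is 1 - 3/327 = 0.991 at the 82 df of a pooled session-level test, a bias of about 1%. With 20 children (18 df) it is 1 - 3/71 = 0.958, about 4%, which is small beside a half-width of 0.89.

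**Conclusion.** The point holds as a matter of interpretation and reporting. Read naturally, the rule can place an effect up to one step too high, calls a near-zero effect small and has no label above 0.80. Read the other way, it leaves the boundaries undefined. Either way it needs rewriting.

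The missing interval matters more than the labels. At d = 0.50 the 95% half-width is about 0.43 at best and about 0.89 with 10 v 10 children, so adjacent labels cannot be told apart. One distinction does survive in the best case: an observed d of 0.80 at 42 v 42 independent sessions has an interval of 0.36 to 1.24, which excludes values up to 0.20. With 10 v 10 children the interval is -0.11 to 1.71, which includes zero.

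These figures rest on assumed splits, the application's count of 20 children, a 95% level and an ICC between 0 and 1. The documents do not show that any reported effect was mislabelled or that any test result is altered by the rule.

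**What to change.** In both the Design and the Statistical Analysis Plan sections, replace the rule with:

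> *For each outcome report the mean difference and the standardised difference, each with a 95% confidence interval that accounts for repeated sessions per child (for example, by child-level means or a child-clustered model). An absolute d below 0.20 is not labelled; 0.20 to below 0.50 is small, 0.50 to below 0.80 medium, 0.80 or more large. Any label is given together with its interval.*

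State which SD is the denominator of d, since child-level means vary less than single sessions. Hedges g and standardising by the average of the two variances are optional.

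Do not go further and bar a label whenever its interval crosses a boundary. At 42 v 42 the interval is at least 2 × 1.96 × sqrt(84/1764) = 0.86 wide against bands of 0.30, so small and medium could never be used.

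The cost is a few sentences and rerun output, with no new data. Some labels drop a step and the intervals will be wide. Relabelling changes no p-value. An interval that allows for clustering may, however, include zero where a session-level t-test rejects, and the report should say so where that happens.
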